**Table 12: Dose Modifications for Parsaclisib for Diarrhea/Colitis**

Parsaclisib Current Dose	Dose Modification
≥ 2.5 mg QD	20 mg QW
1 mg QD	20 mg QW or 10 mg QW
20 or 10 mg QW	Restart next lower dose 10 mg QW or 5 mg QW
5 mg QW	Permanently discontinue

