**Figure 1: Study Design Schema**

**Table 3: Schedule of Activities**

Visit Day (Range)	Screening	Treatment						EOT	Follow-up			Notes
		Cycles 1-3			Cycle 4 Onward				Safety	Disease	Survival	
		Days -28 to -1	Day 1 (± 1 d)	Day 8 (± 1 d)	Day 15 (± 1 d)	Day 22 (± 1 d)	Day 1 (± 1 d)	Day 15 (± 1 d)	EOT + 90 d	Post- Treatment	Last Visit + 12 Wk (± 7 d)	
Administrative procedures												
Informed consent	X											
Contact IRT	X	X				X		X	X			
Inclusion/exclusion criteria	X	X										Verify eligibility on C1D1.
General/disease medical history	X											
Prior/concomitant medications	X		X				X	X				
PJP prophylaxis			X									Required while receiving study treatment and for 2-6 months after the last dose of study treatment.
Dispense parsaclisib		X				X						
Administer parsaclisib		X	X	X	X	X	X					20 mg QD: Cycle 1, 2: Days 1-28.  2.5 mg QD: C3D1 onward Given on-site on PK assessment days.
IRR prophylaxis		X*	X*	X*	X	X	X					*Mandatory for first 3 doses.
Administer tafasitamab		X	X	X	X	X	X					12 mg/kg IV Cycles 1-3: Days 1, 8, 15, and 22 Cycle 4 onward: Days 1 and 15 only
Distribute reminder cards		X	X	X	X	X	X					
Assess treatment compliance			X	X	X	X	X	X				

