### **6.2.1.3. Administration**

### **6.2.2. Parsaclisib**

Participants will self-administer parsaclisib as an oral treatment. Parsaclisib will be administered as 20 mg QD for 8 weeks followed by 2.5 mg QD.

Parsaclisib should be taken at approximately the same time each day.

Administration of parsaclisib will be calendar-based. Delays or interruptions in study treatment will not affect the dosing schedule of parsaclisib; 20 mg QD will be administered only during the first 8 weeks (Days 1-56); all participants will switch to 2.5 mg QD on Day 57.

Treatment with parsaclisib will continue until a criterion is met for treatment discontinuation.

Parsaclisib will be administered in the study clinic on days when blood samples are collected for PK as indicated in Table 3 and Section [8.4](#).

See [Appendix F](#) for instructions to participants for handling parsaclisib.

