**Table 10: Toxicity Management Guidelines for Parsaclisib**

Adverse Event	Recommendation
Chemistry	
AST and/or ALT is Grade 3 ( $> 5.0 \times \text{ULN}$ ). Note: In participants with liver metastasis-related elevations at baseline, contact sponsor to discuss clinical management.	Step 1: Interrupt both tafasitamab and parsaclisib. Monitor weekly until the toxicity has resolved to $\leq$ Grade 1 ( $< 3.0 \times \text{ULN}$ ). Step 2: Restart tafasitamab at the same dose and parsaclisib at next lower dose with medical monitor approval. Monitor as clinically indicated.
Other toxicities	
Diarrhea (Grade 1)	Step 1: Treat with antimotility agents (eg, 2 mg loperamide followed by 2 mg every 4 hours or after every unformed stool) and initiate supportive care. Monitor approximately every 48 hours until resolved. If not improved after 48 hours, treat per guidance for Grade 2.
Diarrhea (Grade 2)	Step 1: Interrupt tafasitamab and parsaclisib. Perform workup for infection (including CMV, Clostridium difficile , etc) immediately. Initiate or continue supportive care. Monitor approximately every 48 hours until resolution. Step 2: If improved within 48 hours and/or infection* is confirmed, restart tafasitamab and parsaclisib at the same schedule and dose after resolved to $\leq$ Grade 1 and continue to monitor. *For infectious diarrhea/colitis, follow institutional standard of care guidelines and restart parsaclisib according to clinical judgment after resolved to $\leq$ Grade 1. Consult with medical monitor if needed. Step 3: If not improved within 48 hours and infection is ruled out, start oral steroids, or consider IV steroids if participant is being given IV fluids. If no improvement with oral steroids, switch to IV steroids. Step 4: When diarrhea resolves to $\leq$ Grade 1, continue supportive care and taper steroids according to institutional standards of care. When taper is complete (eg, no steroid or $\leq 10 \text{ mg/day}$ prednisolone or equivalent) and diarrhea is $\leq$ Grade 1, restart parsaclisib at the next lower dose with approval of the medical monitor. Step 5: If Grade 2 diarrhea reoccurs, treat per guidance for diarrhea ( $\geq$ Grade 3)/noninfectious colitis. Step 6: If $\geq$ Grade 2 diarrhea reoccurs a third time, permanently discontinue parsaclisib.

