**Table 11: Dose Levels for Parsaclisib**

	Dose, C1D1 to C2D28 (Day 1 to Day 56)	Dose, C3D1 to EOT (Day 57 to EOT)
Starting dose	20 mg QD	2.5 mg QD
First dose reduction	10 mg QD	1 mg QD
Second dose reduction	5 mg QD	Not applicable

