## 9.10. Treatment of Overdose

Overdose is not an SAE unless it meets the criteria of an SAE (see Section 9.3).

Overdose of parsaclisib is defined as any daily dose  $> 20$  mg within the first 8 weeks of the study and  $> 2.5$  mg for the rest of the study within a 24-hour time period ( $\pm 4$  hours).

Overdose of tafasitamab is defined as any dose  $> 120\%$  of the protocol-specified dose per single infusion.

Overdose with concomitant medication will not be recorded in the eCRF unless it resulted in an AE.

In the event of an overdose, the investigator should do the following:

- Contact the medical monitor immediately.
- Closely monitor the participant for any AE/SAE and laboratory abnormalities.
- Obtain a plasma sample for PK analysis if requested by the medical monitor.
- Document the quantity of the excess dose as well as the duration of the overdose in the eCRF.

Decisions regarding dose interruptions or modifications will be made by the investigator in consultation with the medical monitor based on the clinical evaluation of the participant. Incyte does not recommend specific treatment for an overdose; treatment of overdose for either study drug should consist of general supportive measures.

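### From Day 57, every weekly parsaclisib dose that Table 12 allows meets the protocol's own overdose definition, and nothing says what a participant on weekly dosing takes at the Day 57 switch

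*Protocol*

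**What the plan says.** **Weekly dosing.** Protocol Section 6.6.2.3 permits, but does not require, parsaclisib to be modified under Table 12 for diarrhea or colitis. Table 12 gives 20 mg weekly from 2.5 mg daily or more. From 1 mg daily the row reads "1 mg QD 20 mg QW or 10 mg QW". A participant already on 20 or 10 mg weekly goes to the next weekly step, 10 or 5 mg.

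**Overdose.** Section 9.10 sets two fixed limits for parsaclisib: a daily dose above 20 mg in the first 8 weeks, and above 2.5 "mg for the rest of the study within a 24-hour time period" (± 4 hours). Neither limit has an exception for a modified dose. The site's required actions include "Contact the medical monitor immediately" and "Document the quantity of the excess dose as well as the duration of the overdose in the eCRF". For tafasitamab, the same section uses a relative limit, more than 120% of the protocol-specified dose per infusion.

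**Day 57.** Section 6.2.2 makes parsaclisib dosing calendar-based and states that "all participants will switch to 2.5 mg QD on Day 57". The Table 3 note repeats "2.5 mg QD: C3D1 onward". Table 11 lists daily reductions by period ("First dose reduction 10 mg QD 1 mg QD" for Days 1-56 and Day 57 onward respectively). The second reduction is 5 mg daily before Day 57 and not applicable after it. Table 11 has no weekly level.

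**The concern.** The protocol offers a dosing option in one place and classes it as an overdose in another. After Day 56 a site using Table 12 correctly would generate urgent contacts and overdose entries for doses given as intended. Such entries blur the record of real dosing errors.

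The Day 57 rule could change a dose actually taken. A participant moved to weekly dosing because of diarrhea or colitis would, on the literal text of Section 6.2.2, go back to daily dosing on Day 57. Section 6.2.2 states no approval step at that point. By contrast, Table 10 requires the medical monitor's approval when parsaclisib is restarted after noninfectious diarrhea or colitis managed with steroids.

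**Working it through.** The plan states no figure of its own here. The check compares the dosing rules with the overdose limits.

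**Inputs.** Weekly doses of 20, 10 and 5 mg (Table 12). Overdose limits of > 20 mg for Days 1-56 and > 2.5 mg afterwards (Section 9.10). Daily doses from Day 57 of 2.5 and 1 mg (Table 11). First 8 weeks = Days 1-56 (Section 6.2.2).

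**Step 1: overdose test.** A weekly dose is taken on one day, so its full amount falls within one 24-hour period. Ratio = weekly dose / 2.5; excess = weekly dose - 2.5.

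| Weekly dose | Above 20 mg (Days 1-56)? | Above 2.5 mg (Day 57 on)? | Ratio to limit | Excess |
|---|---|---|---|---|
| 20 mg | No (equal) | Yes | 20/2.5 = 8 | 17.5 mg |
| 10 mg | No | Yes | 10/2.5 = 4 | 7.5 mg |
| 5 mg | No | Yes | 5/2.5 = 2 | 2.5 mg |

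There is no conflict before Day 57. From Day 57, every Table 12 weekly dose meets the definition.

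**Step 2: Day 57 switch, weekly dosing.** Weekly milligrams on 2.5 mg daily = 2.5 × 7 = 17.5.

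- From 20 mg weekly: 20 to 17.5 mg/week. The total falls slightly, but the schedule returns to daily.
- From 10 mg weekly: 10 to 17.5 mg/week, 17.5/10 = 1.75-fold. Starting from 20 mg daily, this needs two qualifying episodes before Day 57 (20 mg daily to 20 mg weekly to 10 mg weekly).
- From 5 mg weekly: not counted. It would take a third step, and Table 10 stops parsaclisib at a third Grade 2 or higher episode. This reads the Table 12 steps as 20 to 10 and 10 to 5.

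These totals compare milligrams only, not exposure.

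**Step 3: Day 57 switch, reduced daily dosing.** Table 11 pairs 10 mg daily before Day 57 with 1 mg daily after it, so the first reduction has an implied answer. The second reduction, 5 mg daily, has none, because its Day 57 cell is marked not applicable.

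**Step 4: search for an exception.** Sections 6.2.2, 6.6.2.2, 6.6.2.3 and 9.10, and Tables 3, 10, 11 and 12, contain no text that exempts weekly dosing from the overdose limit or from the Day 57 switch.

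**The case against.** The best defense is that the two overdose limits equal the two daily starting doses. Section 9.10 speaks of a daily dose and was evidently drafted with daily dosing in mind. Table 12 is permissive. The medical monitor to be contacted will usually have approved the restart already. Overdose is not in itself a serious adverse event, SAP Appendix A plans no overdose table or listing, and SAP Section 6.5.2 measures compliance against the prescribed dose after modifications. On Day 57, the sentence in Section 6.2.2 follows one about delays and interruptions, so its subject is calendar timing, and specific dose-modification text would normally prevail.

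Most of this limits the consequence but does not remove the conflict. The 24-hour wording catches a weekly dose whatever the intent, and no specific text exists for weekly dosing on Day 57. Weekly dosing is not a slip either: Section 2.1.5.2 describes 20 mg daily for 8 weeks followed by 20 mg weekly, with rituximab, in an earlier study.

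A reader might infer more than the documents support:

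- **Four overdose records per 28-day cycle.** The protocol asks for the quantity and duration of the overdose, which one continuing entry could satisfy.
- **A 2.5-fold increase (1 to 2.5 mg daily) for participants on a reduced daily dose.** At the first reduction, this requires ignoring Table 11.
- **An uncontrolled choice of restart dose.** Table 10 uses wording such as "restart parsaclisib at the next lower dose with approval of the medical monitor" for Grade 2 diarrhea without naming Table 12. However, Section 6.6.2.2 cites both dose tables, Table 12 is titled for diarrhea/colitis, Section 6.6.2.3 points to it, and approval is required. This is a cross-reference gap.
- **A frequent 1.75-fold rise from 10 mg weekly.** Two episodes must be managed and resolved before Day 57. Section 6.6.3 requires discontinuation when a persistent event delays treatment by more than 14 days, unless the sponsor approves a longer delay. The case is remote.

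**Conclusion.** Two stated rules give a wrong result if followed. From Day 57, weekly doses that Table 12 allows are 8, 4 and 2 times the overdose limit and must be handled as overdoses. The Day 57 switch, as written, returns a participant on weekly dosing to 2.5 mg daily.

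The effect is on safety recording and individual dosing. A reader might infer damage to a primary endpoint, but the documents do not support that: the overdose conflict starts after the 28-day DLT window, and neither the response rate nor the definition of a treatment-emergent event depends on an overdose flag. The number affected cannot be derived. Section 2.1.3.1 reports diarrhea/colitis of any grade in 36% of 72 monotherapy participants, so the situation is foreseeable, but that figure does not show how many would reach Table 12 dosing.

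The conclusion rests on a literal reading. It also assumes that the administration cells of Table 6, blank in the public copy, contain no exception.

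**What to change.** - **Section 9.10:** define parsaclisib overdose as a dose above the participant's prescribed dose, in line with the relative definition already used there for tafasitamab. Alternatively, exempt weekly dosing under Table 12. The first option also catches a participant on 1 mg daily who takes 2.5 mg, which the fixed limit misses.
- **Section 6.2.2 and the Table 3 note:** add that participants on weekly dosing under Table 12 stay on their weekly dose past Day 57, and that participants at the first daily reduction move to 1 mg daily per Table 11. The sponsor should state the Day 57 dose for a participant on 5 mg daily.
- **Optional:** cite Table 12 in the two Table 10 restart steps for noninfectious diarrhea/colitis (Grade 2, Step 4; Grade 3 or higher/colitis, Step 3).

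The cost is a few lines at the next amendment, plus one sponsor decision on the 5 mg daily case. No new procedures or data are needed.

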#### **6.6.2.4. Supportive Care Guidelines for Neutropenia and Thrombocytopenia**

Neutropenia and thrombocytopenia are known adverse reactions for tafasitamab and also appear to be PI3K $\delta$  class-effect toxicities. Investigators should ensure that participants understand the need to seek medical care when they have conditions that could become life-threatening in the presence of cytopenias (eg, neutropenic fever or bleeding with low platelet count). Participants should be instructed to report immediately any signs of infection, unexpected bleeding, or sudden, extremely painful headaches.

#### **6.6.2.5. Management of Hypogammaglobulinemia**

Hypogammaglobulinemia induced by depletion of normal B-cells is a potential on-target toxicity of the anti-CD19 mAb tafasitamab. In the clinical development program for tafasitamab, cases of hypogammaglobulinemia have been observed as follows:

- In 3 studies with tafasitamab monotherapy (XmAb5574-01 [NCT01161511] in R/R CLL, MOR208C201 [NCT01685008] in R/R NHL, and MOR208C202 [NCT01685021] in R/R B-cell acute lymphoblastic leukemia), 2 of 141 total participants (1.4%) experienced Grade 2 hypogammaglobulinemia.
- In Study L-MIND (MOR208C203 [NCT02399085] in R/R DLBCL), 5 of 81 participants (6.2%) experienced hypogammaglobulinemia (Grade 1: n = 3, Grades 2 and 3: n = 1 each), with 2 of these cases (2.5%; Grade 1: n = 1, Grade 3: n = 1) occurring during the combination treatment phase with tafasitamab + lenalidomide.

In this study, immunoglobulin levels (IgG, IgA, IgM) will be measured at the timepoints listed in [Table 3](#). Study participants experiencing hypogammaglobulinemia should be managed in accordance with local guidelines.

### **6.6.3. Criteria for Permanent Discontinuation of Study Drug**

The occurrence of unacceptable toxicity will require that the study drug be permanently discontinued. Unacceptable toxicity is defined as follows:

- The occurrence of an AE related to the study drug that, in the judgment of the investigator or the sponsor's medical monitor, compromises the participant's ability to continue study-specific procedures or is considered not to be in the participant's best interest.
- A persistent AE requiring a delay of study treatment for more than 14 days unless a greater delay has been approved by the sponsor.

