### **6.6.2. Criteria and Procedures for Dose Interruptions and Adjustments of Study Drug**

Safety concerns should be discussed with the sponsor immediately upon occurrence or awareness of an event that may affect whether or not a participant should continue on study treatment.

Adverse events that have a clear alternative explanation or transient ( $\leq 72$  hours) abnormal laboratory values without associated clinically significant signs or symptoms may be exempt from dose reduction rules.

Because participants may enter the study with extensive pretreatment and/or severe bone marrow infiltration by the primary disease, dose modifications listed in [Table 8](#) are provided as general guidance. Individual decisions regarding dose reduction should be made using clinical judgment and in consultation with the sponsor's medical monitor, taking into account relatedness of the AE to the study drug(s) and the participant's underlying condition.

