**Table 8: Guidelines for Interruption and Restarting of Study Treatment**

Adverse Event	Value or Grade	Recommendation
Grade 3/4 neutropenia judged to be related to study drugs	ANC decreases to $< 1.0 \times 10^9/L$ for at least 7 days OR ANC decreases to $< 1.0 \times 10^9/L$ with an associated body temperature $\geq 38.5^{\circ}C$ ( $101.3^{\circ}F$ ) OR ANC decreases to $< 0.5 \times 10^9/L$	Interrupt tafasitamab and parsaclisib dosing. Follow CBC every 7 days. Growth factors (eg, G-CSF) and antimicrobial prophylaxis are to be used, as per local guidelines.
	ANC returns to $\geq 1.0 \times 10^9/L$	Provided all other criteria are fulfilled, resume dosing of tafasitamab and/or parsaclisib at the same dose. Monitor as clinically indicated.
Grade 2-4 thrombocytopenia judged to be related to study drugs	Platelet count decreases to $< 75 \times 10^9/L$	Interrupt tafasitamab and parsaclisib dosing. Follow CBC every 7 days.
	Platelet count decreases to $\geq 75 \times 10^9/L$	Provided all other criteria are fulfilled, resume dosing of tafasitamab and/or parsaclisib at the same dose. Monitor as clinically indicated.
Other clinically significant toxicities judged to be related to study drugs	Grade 3	Interrupt the administration of the study drug(s) to which the toxicity is judged to be related to up to 28 days until the toxicity has resolved to $\leq$ Grade 1.
	Toxicities resolve to $\leq$ Grade 1	Restart tafasitamab and parsaclisib at the same doses. If assessed as related to parsaclisib, restart at the next lower dose of parsaclisib (see Table 11). Monitor as clinically indicated.
	Recurrent Grade 3 after 2 dose reductions of parsaclisib	Discontinue tafasitamab and parsaclisib administration and follow-up per Protocol. Exceptions require approval of sponsor.
	Grade 4	Discontinue tafasitamab and parsaclisib administration and follow-up per Protocol. Exceptions require approval of sponsor.

CBC = complete blood count.

Note: If, based on medical judgment, the treating physician considers a laboratory parameter change or AE not to be a study drug-related toxicity, but to represent a natural fluctuation in or progression of the underlying disease, then it is at the physician's discretion and assessment of the individual risk/benefit ratio to determine whether the participant should be dosed. The decision and rationale behind the decision should be documented in the source data.

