### **7.1.1. Reasons for Discontinuation**

Participants **must** be discontinued from study treatment for the following reasons:

- The participant becomes pregnant.
- Progression of disease per Lugano criteria ([Cheson et al 2014](#)) for NHL or the iwCLL criteria ([Hallek et al 2018](#)) for CLL.
- Initiation of new anticancer therapy.
- Consent is withdrawn.

Note: Consent withdrawn means that the participant has explicitly indicated that he/she does not want to be followed any longer; in this case, no further data, except data in the public domain, may be solicited from or collected on the participant.

Participants may choose to discontinue study treatment and remain in the study to be followed for progression and survival; however, this must be appropriately documented in both source documentation and the eCRF.

- Further participation would be injurious to the participant's health or well-being, in the investigator's medical judgment.
- Unacceptable toxicity.
- The study is terminated by the sponsor.
- The study is terminated by the local health authority, IRB, or IEC.

A participant **may** be discontinued from study treatment as follows:

- If, during the course of the study, a participant is found not to have met eligibility criteria, the medical monitor, in collaboration with the investigator, will determine whether the participant should be withdrawn from study treatment.
- If a participant is noncompliant with study procedures or study treatment administration in the investigator's opinion, the sponsor should be consulted for instruction on handling the participant.

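### For a related Grade 3 toxicity held 15 to 28 days without sponsor approval, Table 8 leads to restart and Section 6.6.3 to permanent discontinuation

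*Protocol*

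**What the plan says.** Table 8 (Protocol Section 6.6.2) has a block of rows for drug-related toxicities other than neutropenia and thrombocytopenia. At Grade 3 the instruction is "Interrupt the administration of the study drug(s) to which the toxicity is judged to be related to up to 28 days", with the hold ending when the event has come down to Grade 1 or lower. The next row says "Restart tafasitamab and parsaclisib at the same doses", with parsaclisib one level lower if the event is attributed to it. Neither row mentions sponsor approval. The two rows after that cover Grade 3 events recurring after two parsaclisib reductions, and Grade 4 events. They stop both drugs and add "Exceptions require approval of sponsor". The text introducing the table says that its dose modifications "are provided as general guidance".

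Section 6.6.3 makes permanent discontinuation compulsory for unacceptable toxicity. The second of its two definitions is "A persistent AE requiring a delay of study treatment for more than 14 days unless a greater delay has been approved by the sponsor". Section 7.1.1 lists "Unacceptable toxicity" among the reasons for which a participant must come off study treatment.

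Table 10 has its own pathway for diarrhea or colitis that needs steroids. Once the event has improved, sites are to "continue supportive care and taper steroids according to institutional standards of care". Restart follows when the taper is finished and the medical monitor approves. No maximum length is given for that hold.

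**The concern.** Table 8 and Section 6.6.3 both govern whether a participant goes back on drug after a toxicity hold, and neither refers to the other. A site working from Table 8 sees a 28-day allowance with no approval step. It also sees approval written into other rows of the same table, so it could reasonably conclude that none is needed here. A site working from Section 6.6.3 sees a 14-day limit that only the sponsor can extend.

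At stake is who keeps receiving the combination, and through that some of the tolerability results. Safety and tolerability are the Phase 1b primary objective. SAP Section 8.2.4 tabulates by cohort the participants who permanently discontinued each drug because of a treatment-emergent adverse event. If the stopping rule is applied in two ways, that count partly reflects which section a site followed.

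**Working it through.** No sample size or power figure is involved, so the check is a side-by-side reading.

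**Inputs.** Table 8, Grade 3 row for other related toxicities: hold up to 28 days, no approval condition. Section 6.6.3: limit of 14 days, exception if the sponsor has approved a greater delay. Section 7.1.1: stopping is mandatory once the definition is met.

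**Outcomes for an event that resolves to Grade 1 or lower by the end of the hold:**

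| Length of hold | Longer delay approved by sponsor? | Table 8 | Section 6.6.3 | Agree? |
|---|---|---|---|---|
| 14 days or less | not needed | restart | limit not exceeded | yes |
| 15 to 28 days | yes | restart | exception applies | yes |
| 15 to 28 days | no | restart | permanent discontinuation | **no** |
| more than 28 days | yes | beyond the row's maximum | exception applies | not addressed by Table 8 |
| more than 28 days | no | beyond the row's maximum | permanent discontinuation | no restart under either |

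The opposite outcomes are confined to the third line. The band is 28 − 14 = 14 days, that is days 15 to 28. In Cycles 1 to 3, with weekly tafasitamab, a 14-day hold spans 14 / 7 = 2 scheduled infusions and a 28-day hold spans 28 / 7 = 4.

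**Which drug the limit applies to.** Table 8 holds only the drug or drugs to which the event is related. Section 6.6.3 counts a delay of study treatment, and Section 8.7 explains study treatment as tafasitamab and parsaclisib together. Section 6.6.3 then requires the study drug, in the singular, to be stopped. If parsaclisib alone is held for 20 days while tafasitamab continues, the text does not settle whether the 14-day limit has been passed, or whether one drug or both must stop.

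**Table 10.** The steroid-taper hold has no maximum, so it can pass day 14. Medical monitor approval is required, but for the restart, once the taper is complete. Section 6.6.3 asks for sponsor approval of the delay. The protocol does not say whether the first satisfies the second.

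**Size in the output.** The plan allows 10 evaluable participants per cohort in dose confirmation and up to 20 across both periods. One participant classified differently moves a cohort's discontinuation proportion by 1/10 = 10 percentage points or 1/20 = 5 percentage points. The full analysis set may be somewhat larger, because non-evaluable participants are replaced, and each shift would then be slightly smaller.

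**The case against.** The strongest reply is that the approval clause in Section 6.6.3 already reconciles the two: 28 days is the maximum, and sponsor approval is needed beyond day 14. Section 6.6.2 supports this. It presents Table 8 as guidance, and it tells sites to raise with the sponsor at once any event that may affect whether a participant stays on treatment. A site holding drug for a related Grade 3 event should therefore already be in contact with the party that can approve a longer delay.

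Most of that stands. It makes the joint reading plausible and narrows the conflict to holds without approval. It does not remove it, because Table 8 does not state the joint reading and the protocol nowhere says that Section 6.6.3 overrides the table. A duty to discuss an event is also not the same as recorded approval of a longer delay.

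The consequences for the main results are limited. Most Grade 3 or higher nonhematologic toxicity in Cycle 1 counts as dose-limiting whatever the length of the hold, so the dose-limiting toxicity result is largely insulated. Response rate is analyzed on the full analysis set with no formal test.

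A reader might infer more than the documents support in three ways:

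- **That every hold beyond 14 days forces a permanent stop, or that every Table 8 hold is affected.** The first leaves out the approval exception. The second fails because the 28-day figure belongs to one row; the neutropenia and thrombocytopenia rows state no maximum hold.
- **That the Table 10 steroid-taper holds plainly breach the 14-day limit.** Those restarts already need medical monitor approval. The open question is only whether that approval covers the delay.
- **That many participants would be affected, judging by the COSMOS study.** The protocol reports interruption of tafasitamab in 10 of 11 participants, mainly for infusion-related reactions, and of idelalisib in 9 of 11. Section 2.3 says that most such reactions were handled by pausing the infusion, and idelalisib is not a study drug here. Neither figure measures holds longer than 14 days.

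**Conclusion.** The inconsistency is real and narrow. For a related Grade 3 toxicity in Table 8's category for other events, held for 15 to 28 days without sponsor approval of a longer delay, the protocol directs both restart and permanent discontinuation. With approval the passages agree. The number of participants affected cannot be estimated from the documents. The effect on a cohort's discontinuation rate is 5 to 10 percentage points for each participant handled differently.

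This rests on two readings of undefined words: that an interruption in Table 8 is a delay in the sense of Section 6.6.3, and that an event still requiring a hold after day 14 is persistent. Because one of the two passages is a mandatory stopping rule, the matter should be settled in the text and not left to each site. Nothing here bears on which limit is clinically right.

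**What to change.** Reconcile the passages so that the Grade 3 row of Table 8 and Section 6.6.3:

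- state the same maximum hold and the same sponsor-approval condition, including the day by which approval is needed;
- refer to each other;
- say whether the limit applies to a hold of one drug or only of both, and which drug or drugs must then stop.

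Also state whether medical monitor approval to restart after a Table 10 steroid-taper hold counts as approval of the longer delay under Section 6.6.3. The choice of limit and condition is the sponsor's.

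The cost is a wording change to one table row, one section and a note to Table 10 at the next amendment, and informing sites. It needs no new data and no change to sample size or planned analyses. The one real consequence is that any limit or condition not kept is withdrawn.
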